16.62 Secondary Analyses

16.621 *Acute adverse events:* All patients who were registered to the study and started treatment will be included in the acute adverse event analysis. An acute adverse event is an AE, regardless of attribution, that occurs up to 90 days post-RT. The maximum grade for each type of acute AE will be recorded for each patient. Data will be summarized as frequencies and relative frequencies by treatment arm. Additionally, the relationship of the adverse event(s) to the study treatment will be taken into consideration. Rates will be compared between arms using chi-squared tests.

16.622 *Late adverse events:* All patients who were registered to the study and started treatment will be included in the late adverse event analysis. A late adverse event is an AE, regardless of attribution, that appears or persists after 90 days post-RT and up to 5 years post-RT. The maximum grade for each type of late AE will be recorded for each patient. Data will be summarized as frequencies and relative frequencies by treatment arm. Additionally, the relationship of the adverse event(s) to the study treatment will be taken into consideration. Rates will be compared between arms using chi-squared tests.

16.623 *Locoregional control:* The cumulative incidence of locoregional recurrence will be estimated using a competing risks method (Gooley et al.) by treatment arm. The competing risks will be distant breast cancer recurrence and death. Comparison between arms will employ Fine-Gray regression.

16.624 *Invasive disease-free survival:* i-DFS is defined as the time from registration until the time of invasive disease recurrence (not including DCIS) or death due to any cause. The i-DFS will be estimated with a Kaplan-Meier estimator and curve by treatment arm. Estimates will be given for specific time points along with 95% CIs. Comparison between arms will employ a log-rank test.

16.625 *Disease-free survival:* DFS is defined as the time from registration until the time of disease recurrence or death due to any cause. The DFS will be estimated with a Kaplan-Meier estimator and curve by treatment arm. Estimates will be given for specific time points along with 95% CIs. Comparison between arms will employ a log-rank test.

16.626 *Cause specific survival:* The CSS will be estimated with a Kaplan-Meier estimator and curve by treatment arm. Estimates will be given for specific time

points along with 95% CIs. Comparison between arms will employ a log-rank test.

16.627 *Overall survival:* The OS will be estimated with a Kaplan-Meier estimator and curve by treatment arm. Estimates will be given for specific time points along with 95% CIs. Comparison between arms will employ a log-rank test.

16.631 *Quality of life:* The subscales of the BCTOS, elements from CTCAE-PRO, and other patient reported measures such as fatigue, breast pain, breast shape, and arm related morbidity outlined in the appendix will be summarized as the mean \pm SD and median (minimum value, maximum value). Mixed models will be used to estimate changes at fixed time points as well as compare outcomes between arms.

16.632 *Cosmesis:* The values of the cosmesis instruments (patient self-reported and panel-assessed) will be summarized with the frequencies and confidence intervals of fair or poor cosmesis events at baseline, 2 years, and 5 years by treatment arm. Comparisons between arms will employ chi-squared tests.

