2.2 Secondary Objectives

2.21 To evaluate acute and late toxicity
2.22 To estimate the 5-year locoregional control, invasive disease-free survival and overall survival.

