5.0 Stratification Factors

- 5.1 Treatment modality: Photons vs. spot scanned proton therapy. Of the total 110 patients in this study, fifty-five would be treated in each arm. We will

allow a maximum of 28 patients per arm per treatment modality (photons/x-ray or protons).

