16.0 Statistical Considerations and Methodology

- 16.1 Overview: This is an open label phase III randomized controlled trial to determine the safety of 5 fraction vs 15 fraction radiotherapy after breast conserving surgery. The goal is to determine whether the difference in 24-month complication rates between the experimental arm and the control arm is acceptable. Of interest is whether the experimental arm results in an unacceptable increase in the 24-month complication rate. If it does not, then the experimental arm will be recommended for further study. If the 24-month complication rate is found to be unacceptable, then the recommendation would be to do no further studies of the experimental arm.

- 16.2 Primary and Secondary Endpoints

16.21 Primary Endpoint: The 24-month complication rate, defined as the percentage of women evaluable at 24 months who develop one or more of the following events:

- 1) grade 3 or higher late adverse event OR
- 2) deterioration of cosmesis from excellent/good to fair/poor or from fair to poor at the 24-month evaluation (using the Harvard/NSABP/RTOG Cosmesis Scale)

16.22 Secondary Endpoints:

16.221 Acute and late adverse events including grade ≥ 2 pneumonitis.

16.223 Locoregional control, invasive disease-free, distant recurrence, disease-free survival, cause-specific survival, overall survival.

The following definitions are used for the secondary endpoints of interest:

- *Acute adverse events*: any adverse event, regardless of attribution, that occurs in the first 90 days post-RT.
- *Late adverse events* (up to 5 years post RT): any adverse event that occurred after the first 90 days post-RT and up to 5 years post-RT.
- *Ipsilateral breast tumor recurrence (IBTR)*: this is defined as local recurrence from trial registration as a first event at 5 years. IBTR is defined as both invasive and non-invasive breast cancer involving the same breast parenchyma as the original tumor.
- *Regional recurrence*: invasive breast cancer in the axilla, regional lymph nodes, chest wall, and skin of the ipsilateral breast at 5 years.
- *Distant recurrence*: metastatic cancer that has either been biopsy confirmed or clinically diagnosed as recurrent invasive breast cancer at 5 years.

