16.4 Sample Size Determination

This study requires 100 evaluable women for the primary endpoint analysis (50 evaluable patients per arm).

Ninety-two percent of expected patients completed a 3-year assessment of cosmesis in the randomized phase III study reported by Olivotto et al.⁶¹ Expected was defined as patients who were projected to have had their 3-year follow-up visit based on the date of random assignment and who did not experience recurrence, undergo mastectomy, or die. Therefore to be conservative we will anticipate enrolling 10 (5 per arm) additional patients to account for ineligibility, cancellation, major treatment violations, or other reasons. The maximum projected enrollment is therefore 110 women.

In a large randomized controlled trial Whelan and colleagues compared cosmetic outcomes between conventional and hypofractionated whole breast radiotherapy after lumpectomy. At baseline, 84% of patients in the hypofractionated arm were rated as having good or excellent cosmesis by trained nursing assessment. At 3 years, the percentage was 77%, or an absolute change of 7%.⁶² In the study proposed here, a subset of patients may receive a boost to the lumpectomy cavity which has been associated with a slightly higher risk of fibrosis and adverse cosmesis.^{63,64} Therefore, the sample size proposed for arms 1-2 is based on an assumed value of a 10% complication rate in the control arm. The rate of grade 3 or higher late toxicity in this population is expected to be $\leq 1\%$ (Whelan ASCO 2011). Since the local failure rate and death rate at 2-years in the UK start B trial²⁴ was less than 3% we assume that an additional 10% to account for patients lost to follow, failures, deaths and others should be adequate (Total enrollment of 110 patients).

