16.5 Study Decision Rule and Operating Characteristics

The primary endpoint for this trial is the 24-month complication rate. Complications will be defined as at least one of the following events: 1) grade 3 or higher late adverse event OR 2) deterioration of cosmesis from excellent/good to fair/poor or from fair to poor (using the [Harvard/NSABP/RTOG Cosmesis Scale](#))

The proposed analysis would be to compute the difference in the 24-month complication rate between the experimental arm and the control arm. A one-sided 90% confidence interval (with the upper bound of the interval) was computed by assuming a 10% complication rate in the control arm and a 15% “non-inferiority margin” of the difference (i.e. the maximum the difference can be between the experimental arm and control arm, the largest difference we’re willing to accept). The decision rule would be of the following:

- *Upper bound of the one-sided confidence interval (CI) for the difference (experimental arm 24-month complication rate minus control arm 24-month complication rate) lies above 15% then **recommend that the experimental arm is not investigated further**. The 24-month complication rate of the experimental arm is unacceptably high.*
- *Upper bound of the one-sided confidence interval (CI) for the difference (experimental arm 24-month complication rate minus control arm 24-month complication rate) is less than 15% then **recommend that the experimental arm undergo further investigation**. The 24-month complication rate of the experimental arm is potentially acceptable.*

With 100 evaluable patients, this study has 80% power with a 1-sided alpha of 0.05 to test a null hypothesis that the control arm complication rate is 10% and experimental arm control rate is 25% versus an alternate hypothesis that the complication rate in both arms is 10%. Sample size was computed using PASS v.15 software.

Other considerations: Adverse events, quality/duration of response, and patterns of treatment failure observed in this study, as well as scientific discoveries or changes in standard care will be taken into account in any decision to terminate the study.

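### Sections 16.621 and 16.622 compare adverse event rates only by chi-squared tests of no difference, with no rate difference or interval to show how large an increase has been excluded

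*Combined protocol and SAP*

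**What the plan says.** Section 16.1 gives the purpose of the trial: "This is an open label phase III randomized controlled trial to determine the safety of 5 fraction vs 15 fraction radiotherapy after breast conserving surgery". Among the secondary objectives, 2.21 is "To evaluate acute and late toxicity".

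Sections 16.621 (acute, up to 90 days after radiotherapy) and 16.622 (late, from 90 days to 5 years) record the maximum grade of each AE type per patient and summarise frequencies and relative frequencies by arm. The between-arm inference in both is one sentence: "Rates will be compared between arms using chi-squared tests". Neither section gives a rate difference, an interval, a significance level, a continuity correction or a rule for reading a non-significant result. For acute events the population is stated as: "All patients who were registered to the study and started treatment will be included in the acute adverse event analysis". The late-event population is defined in the same way.

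The primary endpoint is handled differently. Sections 16.5 and 16.6.1 compare the upper confidence bound for the difference in 24-month complication rates with a 15-point margin, described as "the maximum the difference can be between the experimental arm and control arm, the largest difference we’re willing to accept". That composite counts late AEs only at grade 3 or higher, together with cosmetic deterioration.

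**The concern.** The question in this trial is whether 5 fractions is unacceptably more toxic than 15. A test of no difference does not answer it. A p-value above 0.05 can mean that the arms are alike, or that the sample is too small to separate them, and the p-value alone does not say which.

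For late AEs of grade 3 or higher up to 24 months, the primary composite supplies a confidence bound, although only jointly with cosmesis. Three groups have no such cover: all acute AEs, late AEs of grade 1-2, and late AEs between 24 months and 5 years. Grade 2 pneumonitis falls outside the composite too, although section 16.221 names grade 2 or higher pneumonitis in a secondary endpoint.

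At stake is how the toxicity tables can be read. A row with a non-significant p-value and no interval leaves the reader without the figure that matters: the largest increase that the data still allow.

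**Working it through.** **Inputs from the documents**
- Patients per arm: "fifty-five would be treated in each arm" (section 5.1). For the primary endpoint: "This study requires 100 evaluable women for the primary endpoint analysis (50 evaluable patients per arm" (section 16.4).
- Margin 15 points and control rate 10%, both for the 24-month composite (section 16.5).
- Grade 3 or higher late toxicity expected at 1% or less (section 16.4). This is the only AE rate stated as an expectation for this trial.

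**Assumptions**
- Two-sided 5% level and uncorrected Pearson statistic, because 16.621 and 16.622 state neither.
- Control AE rates of 5%, 10%, 20% and 30%. The documents' 10% is the composite rate, so for AEs it is an assumption as well.
- A 15-point increase as a yardstick only.

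**Step 1. The plan's own power figure (primary endpoint).** With 10% in both arms and 50 per arm, SE = √(2 × 0.10 × 0.90 / 50) = 0.060. Power = Φ(0.15/0.060 − 1.645) = Φ(0.855) = 80.4%, which agrees with the stated 80%. No power is stated for the AE comparisons.

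**Step 2. Chance that the chi-squared test misses an increase, 55 per arm.** All 56 × 56 pairs of binomial counts were enumerated, and the probability was summed over pairs with χ² above 3.841. Miss rate = 1 − that sum.

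| Control vs 5-fraction rate | Missed, Pearson | Missed, with continuity correction |
|---|---|---|
| 1% vs 16% | 11% | 23% |
| 5% vs 20% | 31% | 43% |
| 10% vs 25% | 44% | 55% |
| 20% vs 35% | 58% | 66% |
| 30% vs 45% | 62% | 70% |

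Hand check of the 10% vs 25% row by normal approximation:
- The pooled rate is 0.175, so SE₀ = √(2 × 0.175 × 0.825 / 55) = 0.0725.
- SE₁ = √((0.09 + 0.1875) / 55) = 0.0710.
- Power = Φ((0.15 − 1.96 × 0.0725) / 0.0710) = 54.5%, a miss rate of 45.5% against 44.2% exact.

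**Step 3. Smaller increases from the stated 1% rate.** A 15-point rise from 1% is a sixteenfold increase and is usually detected. Smaller rises often are not: 1% to 5% is missed in 82% of trials and 1% to 10% in 42%. The expected count at 1% is 55 × 0.01 = 0.55 per arm, too sparse for the chi-squared approximation.

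**Step 4. What an interval would add.** Take 8/55 (14.5%) against 14/55 (25.5%).
- χ² = 110 × (8 × 41 − 14 × 47)² / (55 × 55 × 22 × 88) = 2.05, p = 0.15.
- The 95% Wilson limits are 7.6% to 26.2% and 15.8% to 38.3%.
- Newcombe lower limit: 0.109 − √((0.2545 − 0.1581)² + (0.2616 − 0.1455)²) = −0.042.
- Newcombe upper limit: 0.109 + √((0.3830 − 0.2545)² + (0.1455 − 0.0756)²) = +0.255.

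The planned row would show p = 0.15. The interval shows that an increase of up to 25.5 points has not been excluded.

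**Step 5. Width to expect.** With equal true rates, the 95% half-width is 1.96 × √(2p(1 − p)/55): 8.1 points at p = 5%, 11.2 at 10%, 15.0 at 20% and 17.1 at 30%.

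**The case against.** The strongest reply is that nothing in the plan hangs on these p-values. The objective is to evaluate toxicity, not to show non-inferiority for each AE. The trial's recommendation rests only on the confidence bound for the composite. Frequencies by arm will be reported, so a reader can compute an interval from them. All of this is correct, and it limits the point to the reporting of secondary safety data.

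Some stronger readings are tempting, and the documents do not support them:

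- **That the sponsor will treat p > 0.05 as proof of safety.** The plan does not say so. It simply leaves the reading of a non-significant test open.
- **That 15 points is the limit set for AEs.** It is defined only for the 24-month composite. The plan sets no unacceptable increase for any AE term.
- **That a non-significant result is likely however much worse the 5-fraction arm is.** In the calculations above the test detects 5% vs 20% in 69% of trials, 10% vs 25% in 56% and 1% vs 10% in 58%. The statement holds only for higher control rates or smaller increases.
- **That the plan has no other comparative information on toxicity.** Grade 3 or higher late AEs enter the primary bound, and patient-reported symptoms are compared by mixed models (16.631). The stopping rules in 16.72 are applied per arm and are monitoring, not a comparison.
- **That AEs are singled out for weaker treatment.** The 95% intervals in 16.624 to 16.627 are for estimates by arm, with log-rank tests between arms. Section 16.632 gives intervals on cosmesis frequencies by arm and again a chi-squared test. None of these plans an interval for the between-arm difference.

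What remains is that, for the clinician-graded events outside the composite, the plan offers a test that cannot say how much extra toxicity has been ruled out.

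**Conclusion.** The point holds as an inexpensive improvement to the AE analyses, not as a flaw in the trial's decision rule. A non-significant chi-squared test on events outside the composite would be weak evidence about comparative safety.

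The size depends on the control rate. For a 15-point increase the miss rate runs from 31% to 62% at assumed control rates of 5% to 30%, and is 11% at 1%. With continuity correction the first range becomes 43% to 70%. The figures use the full 55 per arm. With 50 per arm the Pearson range for 5% to 30% is 34% to 66%.

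**What to change.** In 16.621 and 16.622, replace the chi-squared sentence with wording such as:

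> For each AE type, and for any grade 2 or higher and any grade 3 or higher AE, the difference in rates (5-fraction minus 15-fraction) will be reported with a 95% Newcombe or score confidence interval. The upper limit will be described as the largest increase not excluded. A non-significant test will not be taken as evidence of equal toxicity.

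If p-values are kept, label them descriptive, state the significance level, and use an exact test where cells are sparse.

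The cost is SAP wording and one further column in the AE tables, with no new data or patients. The downside is that many intervals will be wide (step 5) and will look less favourable than a column of non-significant p-values.

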4.0 Test Schedule

	Baseline	Pre-treatment	EOT	Observation ¹²			
	≤120 days prior to start of treatment	≤45 days prior to start of treatment ⁶	Last day of Treatment (+/- 5 days)	12 weeks (+/- 4 weeks) post-treatment	6 months (+/- 2 months)	12 months (+/- 3 months), 24 months (+/- 6 months), 36 months (+/- 6 months), 48 months (+/- 6 months) and 5 years (+/- 6 months) post completion of treatment	Failure*
Consent	X						
Physical exam ¹	X						
Exam/ECOG							
Visit (see Appendix)	X		X ⁸	X		X	X
Visit (see Section)		X ⁹	X ⁸	X		X ¹³	X
Visit ³		X	X	X		X	
Visit (sites 2,3,4) ¹¹		X ⁹	X	X	X	X	X
Visit (see)		X ⁹	X	X		X	X
Specimens							
Initial specimen	X ⁵						X ²
							X ⁷

1. A general history & physical exam should include height and weight (optional at Rochester site)
2. Review of pathology at failure if obtained clinically
3. Photographs can be done at any time before or after treatment at the discretion of the physician
4. Last day of treatment +/- 2 days per discretion of treating physician
5. Outside pathology must be reviewed at treating institution to confirm eligibility within 365 days.
6. Blood pregnancy test to be completed prior to start of treatment on day 1 (for women of childbearing potential only).
7. PET Scan at failure optional
8. Per discretion of treating physician for Arm 2 (5 days)
9. These tests can be done before or up to 3 days into treatment
10. Limited physical exam to include ECOG; weight (optional for Rochester site)
11. As collected clinically
12. Patients that cannot come back to Mayo within the time constraints of the follow-up schedule; efforts to obtain outside records and complete QOL's will occur, however the required items may not be captured.
13. If follow up visit occurred at an outside institution, Cosmetic Assessment will not be required.

*Failure defined as recurrent disease

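### Late adverse events to 5 years are summarised as crude proportions of all treated women, so women whose assessment ends early without a recorded event count as event-free and late toxicity is modestly understated

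*Combined protocol and SAP*

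**What the plan says.** Section 16.622 sets the denominator: "All patients who were registered to the study and started treatment will be included in the late adverse event analysis". A late AE is one that "appears or persists after 90 days post-RT and up to 5 years post-RT". Each woman is reduced to one value per AE type: "The maximum grade for each type of late AE will be recorded for each patient". The reporting is then "Data will be summarized as frequencies and relative frequencies by treatment arm", and "Rates will be compared between arms using chi-squared tests". The section names no censoring, person-time, minimum follow-up or missing-data rule for late AEs.

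Other sections show that assessment will be incomplete:

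- Section 4.0, footnote 12, on women who cannot return within the visit windows: "efforts to obtain outside records and complete QOL's will occur, however the required items may not be captured".
- Section 16.4 cites a randomized trial in which 92% of the women expected had a 3-year cosmesis assessment. It adds 10 women to 100 for loss, failures, deaths and other reasons.
- Sections 13.1 and 13.2 move women who recur, or who stop observation for other reasons, to event monitoring. As the form table in Section 18.1 reads, only the patient status form is marked for that phase.

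The next subsection, 16.623, does allow for incomplete follow-up: "The cumulative incidence of locoregional recurrence will be estimated using a competing risks method", and "The competing risks will be distant breast cancer recurrence and death". Sections 16.624 to 16.627 use Kaplan-Meier estimates.

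**The concern.** A maximum grade over whatever follow-up exists treats a woman last assessed at 12 months without an event like one observed event-free for 5 years. Both add one to the denominator and nothing to the numerator. No sentence calls the first woman event-free; it follows from the fixed denominator. The table would be read as a 5-year late toxicity rate but would sit below it.

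For a regimen whose safety is the question, that is the less cautious direction. Equal loss in both arms also shrinks a real difference, and unequal loss can create a small false one. The plan already uses suitable methods for recurrence and survival, so the gap for late toxicity is easy to close.

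**Working it through.** **The plan's own figure.** None is given for late AEs. The stated sample size concerns the primary endpoint. It reproduces: with 10% in both arms, a 15-point margin and 50 per arm, the standard error is √(2 × 0.1 × 0.9 / 50) = 0.06, and 0.15/0.06 − 1.645 = 0.855, so power is 80.4%. It has no bearing on this point.

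**Inputs.**

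- Arm size: 55 (Section 5.0).
- Window: 5 years (16.622), modelled from time 0 for simplicity.
- Late AE risk p by 5 years: the documents give only 1% or less for grade 3+ (16.4). For commoner events I assume 10%. The 10% in 16.4 and 16.5 is a different quantity, the composite complication rate.
- Loss L by 5 years: not given, so I assume 10% to 30%. Extrapolating 8% missing at 3 years at a constant rate gives 1 − 0.92^(5/3) = 13%.

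**Expected crude proportion.** With constant hazards for AE onset, l = −ln(1 − p)/5, and loss, m = −ln(1 − L)/5:

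crude = l/(l + m) × [1 − (1 − p)(1 − L)]

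For p = 10% and L = 10%, l = m, so crude = 0.5 × (1 − 0.81) = 9.5%. For L = 20%, l = 0.0211 and m = 0.0446, so crude = 0.321 × 0.28 = 9.0%.

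| Loss by 5 years | Crude, true risk 10% | Crude, true risk 1% |
|---|---|---|
| 10% | 9.5% | 0.95% |
| 13% | 9.35% | 0.93% |
| 20% | 9.0% | 0.90% |
| 30% | 8.4% | 0.84% |

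The relative shortfall is about half the loss fraction. Spreading loss evenly over the 5 years instead gives 9.5%, 9.0% and 8.5% at 10%, 20% and 30% loss.

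**Effect on the comparison.** At 20% loss in both arms, a true 10% versus 20% appears as 9.0% versus 18.0%. With equal true risk of 10%, loss of 10% in one arm and 30% in the other gives 9.5% versus 8.4%, a false difference of about 1 point. Loss of 5% versus 20% gives about 0.8 points.

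**Against sampling error.** At a 10% rate the standard error is √(0.09/55) = 4.0 points per arm and √(2 × 0.09/55) = 5.7 points for the difference. The 0.5-point shortfall at 10% loss is 55 × 0.005 = 0.3 of a woman per arm.

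**Deaths only.** Put the death hazard in place of m. With a net risk of 10% and 5% deaths, the crude proportion is 9.75%. That is exactly the cumulative incidence with death as a competing risk, so there is no bias.

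**Does the fix work?** I simulated 4,000 arms of 55 with 10% AE risk, 5% deaths and 20% loss. The true cumulative incidence was 9.75%, the mean crude proportion 8.7%, and the mean Aalen-Johansen estimate, with death as a competing risk, 9.7%.

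**The case against.** The strongest reply is that the effect is too small to matter. A bias of 0.5 to 1.5 points sits beside a standard error of 5.7 points for the difference. Section 16.622 is a secondary summary with no decision rule. The documents' own figures (92% at 3 years, a 10% allowance) point to the low end of the loss range. At the expected grade 3+ rate the shortfall is about 0.05 to 0.16 points. An acute effect persisting past day 90 counts as late at the next assessment, when few women have been lost, so a constant hazard overstates the bias for such events. All of this stands and limits the point to a cheap improvement.

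A reader might infer more than the documents support:

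- **That women who die are also miscounted.** A woman who dies without a late AE can never have one. Leaving her in the denominator is right for a cumulative incidence.
- **That every lost woman counts as event-free.** A late AE recorded before loss still counts.
- **That the safety decision is biased.** The decision rests on the 24-month complication rate among women evaluable then (16.21, 16.6.1), which does not use this denominator.
- **That the shortfall is large because follow-up will be short at analysis.** With follow-up spread evenly over 2 to 4 years, the crude figure would be about 6.1% against a 5-year risk of 10%. Section 16.8 puts primary completion at 48 months after opening, with the last patient at 24 months. However, the plan does not say that late AEs will be reported then, so this is only an illustration.
- **That the arms will lose women at different rates.** Nothing in the documents suggests it.
- **That AE collection certainly ends at recurrence.** A note in 18.1 asks for yearly follow-up after recurrence. It does not say on which forms.

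**Conclusion.** The point holds as a modest weakness of a secondary analysis. Followed as written, 16.622 understates 5-year late toxicity by roughly half the fraction of women whose assessment ends early. At an assumed 10% risk, that means 9.5% at 10% loss, 9.0% at 20% and about 8.5% at 30%. The gain from correcting it lies with grade 2+ events.

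The size rests on an assumed 5-year risk, assumed loss rates, constant hazards, and loss unrelated to toxicity. The direction does not depend on the particular loss rate: any early end of assessment, other than by death, among women still at risk of a first late AE lowers the crude proportion below the 5-year cumulative incidence.

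**What to change.** Keep the maximum-grade table in 16.622 as description, and add:

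- The cumulative incidence of grade 2+ late AEs at 2 and 5 years by arm, counted from day 90. An AE persisting at day 90 counts as an event at the first later assessment.
- Death as a competing risk, censoring at the last AE assessment, and numbers at risk shown.
- A comparison of arms by Gray's test or Fine-Gray regression, for grade 2+ only.
- Grade 3+ late AEs reported descriptively. At 1% of 110 women, about one event is expected (110 × 0.01 = 1.1), too few for a regression.

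The cost is a little more analysis. Onset will be known only to the visit interval, and visits are yearly after the first year. An occurrence date appears in the example worksheet in 10.31, whereas Section 10.4 shows the listed AEs only as graded at baseline and each evaluation. The visit date may therefore have to stand in for onset.
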